Investigational ixazomib (expired or end of study) should be destroyed on site according to the institution's standard operating procedure. Be sure to document removal and destruction on drug accountability logs.

Lenalidomide Administration

Lenalidomide will be provided in accordance with the lenalidomide REMS® program of Celgene Corporation. Per standard lenalidomide REMS® requirements, all physicians who prescribe lenalidomide for research subjects enrolled into this trial must be registered in and must comply with all requirements of the lenalidomide REMS® program. Prescriptions must be filled within 7 days. Only enough lenalidomide for one cycle of therapy will be supplied to the patient each cycle. Unused lenalidomide will be counted and documented by each site.

Subjects randomized to the experimental arm will receive lenalidomide as follows:

- Cycles 1-4: Lenalidomide will be administered on Days 1-21 at a dose of 25 mg.
- Cycles 5-12: Lenalidomide will be administered on Days 1-21 at the best tolerated dose.

Lenalidomide should be taken in the evening at approximately the same time each day. Lenalidomide is taken with water on a full or empty stomach. Subjects should not break, chew

or open capsules. Missed doses can be taken as soon as the patient remembers as long as it is less than 12 hours since the scheduled time. If it has been more than 12 hours, the dose should be skipped. Vomited doses will not be made up. Subjects should be instructed to never take lenalidomide past Day 21 of each cycle.

Dexamethasone Administration

Dexamethasone will ideally be best administered in the morning with a meal 2 hours before Ixazomib. If this is not possible, dexamethasone will be administered with a meal and at least 1 hour after ixazomib dose on days that they coincide (Days 1, 8, 15), as follows:

- Cycles 1-4: 40 mg PO per dose Days 1, 8, 15 and 22
 - Dexamethasone may administered as a split schedule of 20 mg PO or IV (pre-ixazomib during weeks 1-3 when ixazomib is administered) on Days 1, 2, 8, 9, 15, 16, 22, and 23 after discussion with the Lead Principal Investigator.
- Cycles 5-12: Dexamethasone discontinuation
 - Low dose of dexamethasone up to 20 mg per dose weekly on days 1, 8, 15, and 22 is allowed based on investigator determination of best tolerability of regimen.

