Dosage adjustments for hematologic toxicity are outlined in Table 6-5

Table 7-5 Ixazomib and Lenalidomide Dose Adjustments for Hematologic Toxicities^{a, b}

Criteria	Action
Within-Cycle Dose Modifications	
 • Ixazomib dose and lenalidomide should be withheld. • Complete blood count (CBC) with differential should be repeated at least twice weekly until the ANC has exceeded the pre-specified values (see Section 6.3.1) on at least 2 occasions. • If neutropenia resolved to <Grade 2: 
 ◦ Lenalidomide decrease 1 dose level ◦ Ixazomib – resume at its most recent dose if ANC recovered prior to next planned dose and resume planned treatment cycle
Day 1 of Cycle Dose Modifications	
 • If neutropenia is the only toxicity for which a dose reduction is required, G-CSF may be used prophylactically, as per ASCO guidelines, for the subsequent cycle and dose maintained • For each subsequent occurrence of the same level of neutrophil count decrease, hold lenalidomide treatment and upon recovery of ANC to >1,000/mm³ resume as follows: 
 ◦ 1st occurrence – decrease lenalidomide 1 dose level ◦ 2nd occurrence – decrease ixazomib 1 dose level ◦ 3rd occurrence – decrease lenalidomide by 1 additional dose level; do not dose below 5mg daily
Grade 4 neutropenia (<500/mm³)	
Within Cycle Dose Modifications	
 • Ixazomib dose and lenalidomide should be withheld. • Complete blood count (CBC) with differential should be repeated at least twice weekly • If neutropenia resolved to <Grade 2 within the cycle: 
 ◦ Lenalidomide decrease 1 dose level below current dose level ◦ Ixazomib if prior to next planned dose, decrease 1 dose level

Dosage adjustments for hematologic toxicity are outlined in Table 6-5

Table 7-5 Ixazomib and Lenalidomide Dose Adjustments for Hematologic Toxicities^{a, b}

Criteria	Action
Day 1 of Cycle Dose Modifications	
 • Use of G-CSF as above • For each subsequent drop $<1,000/\text{mm}^3$ and recovery to $>1,000/\text{mm}^3$, decrease lenalidomide one dose level less than the previous dose, but do not dose below 5 mg daily

a) Both drugs may be reduced at the same time at the investigator's discretion
b) Doses held during a treatment cycle are not to be replaced

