Grade 4 non-hematologic toxicities judged to be related to ixazomib	
 Consider permanently discontinuing ixazomib 	Exceptions are cases in which the investigator determines the patient is obtaining a clinical benefit
Delay of >2 weeks in the start of a subsequent cycle due to lack of toxicity recovery related to ixazomib	Hold ixazomib until resolution Reduce ixazomib 1 dose level	The maximum delay before treatment should be discontinued will be 3 weeks. If the maximum delay has been exceeded, resuming treatment can be considered after discussion with overall PI if clinical benefit is determined

Once ixazomib, lenalidomide, and/or dexamethasone are reduced for any toxicity, the dose may not be re-escalated.

Lenalidomide dose adjustments are allowed based on clinical and laboratory findings. Sequential lenalidomide dose reductions to 15 mg daily, 10 mg daily, and 5 mg daily are recommended for toxicity as indicated in Table 6-7.

Table 7-7 Lenalidomide Lenalidomide Dose Modifications Due to Non-Hematologic Toxicities

Adverse Event (Severity)	Action
Other Grade 3/4 toxicities	
 Hold lenalidomide treatment until toxicity has resolved to \leq Grade 1 or patient's baseline; restart at the next lower dose level (5mg less than the previous dose) 
 Do not dose below 5 mg daily
Rash	
 Non-blistering Rash, Grade 3 Non-blistering Rash, Grade 4 Desquamating (blistering rash) – Any grade 
 Hold lenalidomide and follow weekly. If the toxicity resolves to \leq Grade 1 prior to Day 21 of the current cycle, restart at 1 dose decrement and continue the cycle until Day 21 of the current cycle. Discontinue lenalidomide treatment Discontinue Lenalidomide treatment
Erythema multiforme \geq Grade 3	
 Discontinue lenalidomide treatment
Sinus Bradycardia / other new onset cardiac arrhythmia not present at baseline or deterioration of pre-existing cardiac arrhythmia	
 \leq Grade 2 \geq Grade 3 
 Hold lenalidomide, follow at least weekly. If the toxicity resolves to \leq Grade 1 prior to Day 21, restart at 1 dose decrement and continue the cycle until Day 21. Discontinue lenalidomide treatment

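### The sentence introducing Table 7-7 skips the 20 mg lenalidomide step that Tables 7-2 and 7-7 give for a patient on 25 mg

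*Combined protocol and SAP*

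**What the plan says.** Section 7.2.1 sets the experimental-arm dose for Cycles 1-4: "Lenalidomide will be administered on Days 1-21 at a dose of 25 mg". From Cycle 5 the best tolerated dose is used.

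The protocol then describes reductions from 25 mg in three places:

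- **Table 7-2 (section 7.3), 25 mg row:** 20 mg, 15 mg, 10 mg, 5 mg, then 5 mg every other day.
- **Sentence above Table 7-7 (section 7.3.1):** "Sequential lenalidomide dose reductions to 15 mg daily, 10 mg daily, and 5 mg daily are recommended for toxicity". It refers the reader to Table 6-7, a number that the current document no longer uses for any table.
- **Table 7-7, row for other Grade 3/4 toxicities:** "restart at the next lower dose level (5mg less than the previous dose", with the limit "Do not dose below 5 mg daily".

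Just before that sentence comes the rule "Once ixazomib, lenalidomide, and/or dexamethasone are reduced for any toxicity, the dose may not be re-escalated".

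**The concern.** For a patient on 25 mg, one section gives two different first reductions. The tables lead to 20 mg and the sentence leads to 15 mg. Every experimental-arm patient is planned to start on 25 mg, so the conflict sits at the first reduction any of them would have. A site that reads the sentence rather than the tables could take a patient down two levels for one toxicity, and could not reverse it under the re-escalation rule. Section 4.4 plans for 8 centers, so different sites could read it differently.

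**Working it through.** **Inputs.** 25 mg on Days 1-21 (section 7.2.1); first step 20 mg (Table 7-2); step size 5 mg (Table 7-7); first listed reduction 15 mg (sentence above Table 7-7); 28-day cycles, at most 12.

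**Step 1: do the two tables agree?** Table 7-7: 25 - 5 = 20 mg. Table 7-2 prints 20 mg. They agree, and continue to agree through 15, 10 and 5 mg. Only the sentence differs. It reaches 5 mg daily in 3 steps, where Table 7-2 takes 4.

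**Step 2: could the sentence refer to something else?**

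- *The control arm?* No. Table 7-4 starts at 15 mg or 10 mg, so no control patient is reduced to 15 mg.
- *A patient starting at 20 mg?* No. Neither arm has a nominal 20 mg dose.
- *A limit set by capsule strength?* Section 7.1 lists 5, 10, 15 and 25 mg capsules and no 20 mg capsule. This may explain the wording, but 20 mg can be made up as 10 + 10 or 15 + 5.

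**Step 3: size per cycle (dose x 21 days).**

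| Dose | mg per cycle | Cut from 25 mg |
|---|---|---|
| 25 mg | 25 x 21 = 525 | none |
| 20 mg (tables) | 20 x 21 = 420 | 105/525 = 20% |
| 15 mg (sentence) | 15 x 21 = 315 | 210/525 = 40% |

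The gap between the two readings is 420 - 315 = 105 mg per cycle, and 105/420 = 25%.

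**Step 4: upper bound over the treatment course.** If the reduction takes effect at cycle k and neither patient is reduced again through Cycle 12, the gap is 105 x (13 - k):

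- k = 2: 105 x 11 = 1,155 mg
- k = 5: 105 x 8 = 840 mg
- k = 12: 105 x 1 = 105 mg

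These are ceilings. If the patient on 20 mg later steps to 15 mg while the other stays at 15 mg, the gap closes from then on.

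**Step 5: reach of the sentence.** It introduces Table 7-7, which covers non-hematologic toxicity. Platelet and neutrophil reductions are set by Table 7-5 in dose levels, and Table 7-2 defines those levels. The calculation above therefore applies to non-hematologic reductions only.

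**The case against.** The best defense is that the sentence contains its own remedy. It recommends rather than commands, and it defers to a table. Once the outdated number is read as Table 7-7, that table gives 20 mg, and Table 7-2 prints the same figure. A careful site would end at 20 mg. This stands as far as it goes: the text supports only that a site *could* give 15 mg, not that it would.

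The second defense is that section 7.3 requires discussion with the Lead Principal Investigator for any modification that departs from the protocol. This helps less, because both figures are in the protocol and a site using either could believe it complies.

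A reader might infer two further errors from the same tables. The documents support neither.

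- **That the 5 mg daily floor was left out of the within-cycle neutropenia rules by mistake.** The unevenness in Table 7-5 is real. The Grade 4 Day 1 rule reads "decrease lenalidomide one dose level less than the previous dose, but do not dose below 5 mg daily", while the Grade 4 within-cycle rule reads "Lenalidomide decrease 1 dose level below current dose level" with no floor. For Grade 3, the floor is only on the third-occurrence Day 1 line: "decrease lenalidomide by 1 additional dose level; do not dose below 5mg daily". But Table 7-5 treats within-cycle and Day 1 events differently in other ways, and Table 7-2 lists 5 mg every other day as a valid level, so the within-cycle rule has a defined result. Nothing shows which version was intended. Adding the floor would also remove a reduction step for a patient with an ANC below 500/mm³, which is a clinical trade-off and not an editorial one.
- **That a patient already on every-other-day dosing is caught between the floor and the ban on re-escalation.** The floor limits how far a reduction may go. It does not order an increase for someone already lower, so the two rules do not collide. Section 7.3 also provides for discontinuation at the investigator's judgment and for deviations approved by the Lead Principal Investigator.

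**Conclusion.** The sentence above Table 7-7 is wrong for a patient on 25 mg: it omits the 20 mg step and carries an outdated table number. A site relying on it for a non-hematologic toxicity could give 315 mg instead of 420 mg per cycle, 25% less, with no way back up. The per-cycle figure assumes full dosing on Days 1-21. The cumulative ceilings also assume no later reduction. The documents give no frequency for such reductions, so the expected number of affected patients cannot be stated.

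The severity is minor. No effect on sample size, power or the primary analysis is shown. The uneven 5 mg floor in the neutropenia rules is a question for the sponsor and is not counted here as an error.

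**What to change.** Amend the sentence so that the sequence reads 20 mg, 15 mg, 10 mg and 5 mg daily, and change its reference from Table 6-7 to Table 7-7. This changes one sentence and leaves design, sample size and analysis as they are.

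Also ask the sponsor to state whether the 5 mg daily floor in the Day 1 neutropenia rules is meant to apply within a cycle. The answer is a clinical decision. Whichever way it goes, a short clarification in Table 7-5 would record it.

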- 27) Acute infection requiring systemic anti-infectives, antivirals, or antifungals within two weeks prior to first dose
- 28) Systemic treatment, within 14 days before the first dose of ixazomib, with strong CYP3A inducers (rifampin, rifapentine, rifabutin, carbamazepine, phenytoin, phenobarbital), or use of Ginkgo biloba or St. John's wort.
- 29) Ongoing or active systemic infection, active hepatitis B or C virus infection, or known human immunodeficiency virus (HIV) positive.
- 30) Any serious medical or psychiatric illness that could, in the investigator's opinion, potentially interfere with the completion of treatment according to this protocol.
- 31) Known allergy to any of the study medications, their analogues, or excipients in the various formulations of any agent.

32) Known GI disease or GI procedure that could interfere with the oral absorption or tolerance of ixazomib including difficulty swallowing.
33) Diagnosed or treated for another malignancy within 2 years before study enrollment or previously diagnosed with another malignancy and have any evidence of residual disease. Patients with non-melanoma skin cancer or carcinoma in situ of any type are not excluded if they have undergone complete resection.
34) Patient has \geq Grade 3 peripheral neuropathy or Grade 2 with pain on clinical examination during the screening period.
35) Participation in other clinical trials, with other investigational agents not included in this trial, within 30 days of the start of this trial and throughout the duration of this trial.

Duration of Study:

Subjects will be treated on protocol for 12 months or until disease progression or if lenalidomide and/or ixazomib are permanently discontinued due to intolerance before the end of 1 year. Patients who complete 12 months of protocol treatment will be taken off protocol with management as per PI discretion and standards of care but will continue to be followed for progression, if the patient did not progress on study treatment, and survival.

STUDY OVERVIEW DIAGRAM

SCHEDULE OF EVENTS

Assessment	Screening ²	Cycles 1-12				EOT	Long-term follow-up
		1	8	15	22		
Day	-42 to -1						
Informed Consent+♥	X						
Medical History / Treatment History ¹	X						
Skeletal Survey	X						
ECG ³	X					X	
Physical Exam / ECOG ^{4,5}	X	X				X	
Vital Signs ⁶	X	X				X	
Height ⁷ , Weight, BSA	X	X				X	
24-hour urine ⁸	X	X				X	
Urinalysis	X					X	
C- Reactive Protein	X						
Hematology ⁹	X	X	[X]	[X]		X	

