Treatment modifications due to ixazomib-related AEs are outlined in Table 6-6.

Table 7-6 Ixazomib Treatment Modification (Delays, Reductions, and Discontinuations) Due to Adverse Events (Non-Hematologic Toxicities)

Adverse Event (Severity)	Action on ixazomib	Further Considerations
Peripheral Neuropathy:		
Grade 1 peripheral neuropathy without pain	
 • No action 	Grade 1 signs and symptoms: asymptomatic; without pain or loss of function; clinical or diagnostic observations only [14]
New or worsening Grade 1 peripheral neuropathy with pain or Grade 2	
 • Hold ixazomib until resolution to Grade ≤ 1 without pain or baseline • Reduce ixazomib 1 dose level 	Grade 2 signs and symptoms: Moderate symptoms; limiting instrumental activities of daily living (ADL) [14]
New or worsening Grade 2 peripheral neuropathy with pain or Grade 3	
 • Hold ixazomib until resolution to Grade ≤ 1 without pain or baseline • Reduce ixazomib to next lower dose upon recovery 	Grade 3 signs and symptoms: severe symptoms; limiting self-care ADL; assistive device indicated [14]
New or worsening Grade 4 peripheral neuropathy	
 • Discontinue ixazomib 	

Table 7-6 Ixazomib Treatment Modification (Delays, Reductions, and Discontinuations) Due to Adverse Events (Non-Hematologic Toxicities)

Adverse Event (Severity)	Action on ixazomib	Further Considerations
Grade 2 Rash	
 Follow at least weekly Symptomatic recommendations as per section 6.6 	The investigator and project clinician may discuss considerations for dose modifications and symptom management.
Grade 3 non-hematologic toxicity judged to be related to ixazomib except for the following toxicity: 
 > Grade 3 nausea and/or emesis in the absence of optimal anti-emetic prophylaxis (section 6.7) > Grade 3 diarrhea that occurs in the absence of optimal supportive therapy (section 6.7) Grade 3 fatigue 	
 Hold ixazomib until resolution to Grade < 1 or baseline 
Subsequent recurrence Grade 3 that does not recover to < Grade 1 reduce ixazomib 1 dose level
	Symptomatic recommendations noted in Section 6.7 Monitor closely, take appropriate medical precautions, and provide appropriate symptomatic care

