7.3.1.1 Conditions Not Requiring Dose Reduction

The following conditions are exceptions to the above guidelines.

- Grade 3 nausea, vomiting, or diarrhea (unless persisting more than 3 days with adequate treatment of antiemetics or antidiarrheal agents)
- Grade 3 dexamethasone-related hyperglycemia (see Table 6-8 for guidelines and treatment)

- Grade 1-2 lenalidomide and/or ixazomib-induced rash
- Grade 3 fatigue (unless persisting for > 14 days)
- Alopecia

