Symptomatic measures such as antihistamines or corticosteroids (oral or topical) have been successfully used to manage rash and have been used prophylactically in subsequent cycles. The use of a topical, IV, or oral steroid (e.g., prednisone \leq 10 mg per day or equivalent) is permitted. Management of a Grade 3 rash may require intravenous antihistamines or corticosteroids. Administration of ixazomib (and/or other causative agent if given in combination) should be modified per protocol and re-initiated at a reduced level from where rash was noted (also, per protocol).

In line with clinical practice, dermatology consult and biopsy of Grade 3 or higher rash or any SAE involving rash is recommended. Prophylactic measures should also be considered if a

patient has previously developed a rash (e.g., using a thick, alcohol-free emollient cream on dry areas of the body or oral or topical antihistamines). A rare risk is Stevens – Johnson Syndrome, a severe and potentially life-threatening rash with skin peeling and mouth sores, which should be managed symptomatically according to standard medical practice. Punch biopsies for histopathological analysis are encouraged at the discretion of the investigator.

Thrombocytopenia

Blood counts should be monitored regularly as outlined in the protocol with additional testing obtained according to standard clinical practice. Thrombocytopenia may be severe but has been manageable with platelet transfusions according to standard clinical practice. Ixazomib administration should be modified as noted as per dose modification recommendations in the protocol when thrombocytopenia occurs (see Table 6-2). Therapy can be reinitiated at a reduced level upon recovery of platelet counts. A rare risk is thrombotic thrombocytopenic purpura (TTP), a rare blood disorder where blood clots form in small blood vessels throughout the body characterized by thrombocytopenia, petechiae, fever, or possibly more serious signs and symptoms. TTP should be managed symptomatically according to standard medical practice.

Neutropenia

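### Table 7-7 discontinues lenalidomide for blistering rash of any grade, while section 7.3.1.1 excepts drug-induced Grade 1-2 rash without excluding blistering, so one event has two instructions

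*Combined protocol and SAP*

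**What the plan says.** **Table 7-7 (section 7.3.1), rash row.** The row has three categories and three actions. The first category is "Non-blistering Rash, Grade 3", for which lenalidomide is held and may be restarted one decrement lower. The second is non-blistering rash of Grade 4. The third is "Desquamating (blistering rash) – Any grade". The action for the second and the third is to discontinue lenalidomide.

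**Section 7.3.1.1, Conditions Not Requiring Dose Reduction.** This section comes after all the dose-modification tables and opens with "The following conditions are exceptions to the above guidelines". One of its bullets is "Grade 1-2 lenalidomide and/or ixazomib-induced rash". The bullet does not mention blistering or desquamation.

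**Section 7.3, opening text.** Ixazomib and/or lenalidomide are to be discontinued for any toxicity that the lead or treating investigator judges to warrant it. Temporary holds for treatment-related toxicity are at the treating investigator's discretion.

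**Section 7.6, rash paragraphs.** The causative agent is to be modified as the protocol directs and restarted at a lower level. That sentence gives no grade limit.

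**Protocol Summary, Duration of Study.** Protocol treatment ends early "if lenalidomide and/or ixazomib are permanently discontinued due to intolerance before the end of 1 year".

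**Section 8.1.4, Populations for Analysis.** Apart from a replaced category of patients who decline treatment for reasons unrelated to toxicity or efficacy, anyone who stops before 12 cycles is a treatment failure for the primary endpoint.

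**The concern.** A site that sees a mild or moderate blistering rash, and attributes it to study drug, finds one instruction in the table and a different one in the section labelled as an exception to the table. Two sites could handle the same event differently, and each could cite the protocol.

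The first stake is safety and consistency of conduct: the protocol singles out blistering rash for action at any grade, then appears to withdraw that for the lower grades. The second is the primary endpoint. Under the table, the patient leaves protocol treatment and is scored as a failure. Under the exception, the same patient may continue and be scored on the 12-month marrow. The trial is open-label, so the choice would be made by staff who know the arm.

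**Working it through.** No sample size, power or event count enters this point, so there is no planned figure to reproduce. The check compares the texts.

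**Step 1: is the pairing in Table 7-7 secure?** The table is flattened in the available copy, so categories and actions were matched by order. The actions read hold, discontinue, discontinue. Since the second and third are both discontinuations, swapping those two would not change the result. Blistering rash is matched to discontinuation.

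**Step 2: set the two rules side by side for rash attributed to lenalidomide and/or ixazomib.**

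| Rash | Table 7-7, rash row | Section 7.3.1.1 | Same answer? |
|---|---|---|---|
| Non-blistering, Grade 1-2 | no entry | excepted | yes |
| Non-blistering, Grade 3 | hold, then restart lower | not listed | no conflict |
| Non-blistering, Grade 4 | discontinue | not listed | no conflict |
| Blistering, Grade 1-2 | discontinue | excepted | **no** |
| Blistering, Grade 3-4 | discontinue | not listed | no conflict |

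One cell conflicts. Non-blistering entries start at Grade 3, so the blistering entry is the only one in that row that acts on Grade 1-2. It is therefore the only entry in the row that the 7.3.1.1 bullet can touch.

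**Step 3: does any text rank the two rules?** None was found. The opening sentence of 7.3.1.1 points towards the exception. The explicit reference to all grades in Table 7-7 points towards the table. Section 7.6 does not settle it: its restart at a lower level matches neither a discontinuation nor an exemption from reduction.

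**Step 4: path to the primary endpoint.** "Discontinue lenalidomide treatment" carries no word such as permanently, but the same row uses a hold for temporary stops, so a permanent stop is the natural reading. On that reading, Duration of Study ends protocol treatment, and section 8.1.4 scores a stop before 12 cycles as failure. With 30 patients per arm, one changed score moves an arm's rate by 1/30 = 3.3 percentage points, and only if that patient would otherwise have been MRD-negative at 12 months.

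**Step 5: can the expected effect be computed?** It would need the frequency of drug-induced Grade 1-2 blistering rash, the share of sites following each rule, and the chance that an affected patient would have become MRD-negative. The documents give none of these for such patients.

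**The case against.** The best case for the existing text is that it has a sensible harmonised reading. The heading of 7.3.1.1 concerns dose reduction, whereas the blistering entry is a discontinuation. Table 7-7 is the more specific rule, since it names blistering and covers all grades. Another bullet in the same list, on hyperglycemia, refers the reader back to the dexamethasone guidance, which suggests that the list works alongside the tables. Section 7.3 also lets the investigator stop or hold drug for any toxicity that warrants it.

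Much of this stands. It shows that the two texts are not equally forceful commands and that nobody is compelled to continue lenalidomide. It does not remove the conflict. The opening sentence of 7.3.1.1 is wider than its heading and labels the general bullet as the exception. Discretion permits stopping, but it does not say whether stopping is required.

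A reader might also infer stronger points that the documents do not support:

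- **That every Grade 1-2 rash is exempt and the patient stays at full dose.** The bullet covers only rash induced by lenalidomide and/or ixazomib, and the heading says only that reduction is not required.
- **That the protocol calls this reaction life-threatening.** Section 7.6 says "A rare risk is Stevens – Johnson Syndrome, a severe and potentially life-threatening rash with skin peeling and mouth sores". That describes Stevens-Johnson Syndrome, not a Grade 1-2 blistering rash, and 7.3.1.1 does not name the syndrome.
- **That the ixazomib rule contradicts the lenalidomide rule.** Table 7-6 handles Grade 2 rash with weekly follow-up, symptomatic care and optional discussion of dose changes. Different rules for different drugs are a design choice.
- **That the effect is large or falls mainly on the IRd arm.** Section 1.3 reports rash of all grades in about 50% of patients, and more often with the combination. Applying this to 30 patients would give 15, but that figure counts all rash. It says nothing about the blistering Grade 1-2 subset.

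**Conclusion.** The concern holds in a narrow form. For a drug-induced blistering rash of Grade 1 or 2, Table 7-7 and section 7.3.1.1 give different lenalidomide instructions, and the protocol does not say which prevails. The overlap is one cell of the grade-by-type grid, and the discretion in section 7.3 softens it.

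The endpoint consequence is possible but not quantifiable. It rests on reading the Table 7-7 action as permanent and as a discontinuation for intolerance, and on the affected patient being one who would otherwise have reached MRD negativity. No claim is made about how often this happens or about the trial's power. The point should be fixed because it is a safety instruction that two careful readers can apply differently. It does not call the design into question. Which instruction is clinically right is outside this review.

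**What to change.** In one amendment, reconcile the rash row of Table 7-7 with the rash bullet of section 7.3.1.1:

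- State in the 7.3.1.1 bullet whether the exception includes blistering (desquamating) rash.
- Make the Table 7-7 entry agree, so that each type and grade of rash has exactly one lenalidomide instruction.
- Check that the rash wording in section 7.6 on modifying and restarting the causative agent is consistent with the result.

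The sponsor's clinicians decide the content of the rule. The cost is wording in one table row and one bullet, plus a consistency check of section 7.6. It adds no visits, assays or patients.
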